2.6 Data Analyses

Descriptive statistics will be used to present and summarize the data collected in the clinical study. Frequency distributions and cross tabulations will be presented for discrete variables. Means, standard errors, and ranges will be presented for continuous variables.

Classification of "HF hospitalization" and "cardiovascular death" events for use in primary endpoint 1, secondary endpoint 2, and secondary endpoint 3 analyses will be determined by a Clinical Events Committee (Section 5.1.1.).

For primary endpoint 1, the lower, one-sided, exact 97.5% bound for the observed proportion of responders ("improved") would have to exceed 3% for rejection of the null hypothesis. Additionally, descriptive statistics will be provided for observed

changes in NYHA class and frequency tabulations provided for the other components of the Clinical Composite Score.

The AE-free rate calculated for secondary endpoint 1 will be based on the total number of subjects with at least one MPP related adverse event requiring additional invasive intervention to resolve. For the secondary endpoint analysis, the AE classification, category, resolution, and relation to the MPP feature for each individual event will be determined by the Clinical Events Committee (CEC) (Section 5.1.1). All adverse events which the CEC determines the event is related or possibly related to the MPP feature will be included in the secondary endpoint 1 analysis. Adverse events with a final CEC adjudicated relation of not related or unknown will not contribute to or be included in the evaluation of the secondary endpoint.

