2.6.2 MPP Sub-Study Analysis Population

The primary and secondary endpoint analyses will be conducted according to the intention-to-treat principle (ITT) utilizing all available data from fully enrolled subjects. Subjects are expected to remain programmed with the MPP feature ON from MPP enrollment through the completion of the sub-study. Subjects who have the MPP feature permanently turned OFF prior to completion of the sub-study will be required to report a protocol violation; however, these subjects will be included in the analysis population. All available data from subjects that undergo a pulse generator change and no longer have an MPP eligible device will be included in the analysis. Subjects may have the MPP feature temporarily turned OFF due to a lead revision procedure and these short durations with MPP will not be reported as a protocol violation.

Any QP ExCELS subject that does not enroll into the MPP sub-study but receives MPP due to the physician's determination will not be analyzed towards the MPP study endpoints.

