5.1.1 Clinical Events Committee – MPP Sub-Study Events

The QP ExCELS Clinical Events Committee (CEC) described in Section 5.1 will adjudicate all adverse events that require additional invasive intervention to resolve which may be related to the MPP feature. These events include any software issues related to MPP programming or any adverse event that occurs while MPP is enabled and that may be attributed to the use of the MPP feature. The CEC will indicate whether the adverse event is related, possibly related, not related, or has an unknown relation to the MPP feature.

In addition, the CEC will adjudicate all deaths reported while participating in the MPP sub-study and classify each death as cardiovascular, vascular, non-cardiovascular/vascular, or unknown.

The CEC will adjudicate all reported protocol-defined hospitalizations while a subject is enrolled in the MPP sub-study. Hospitalization events will be classified as cardiovascular, vascular, non-cardiovascular/vascular, or unknown. Additionally, hospitalizations classified as cardiovascular will be further classified as a HF hospitalization, non-HF hospitalization, or unknown. Hospitalization events reported by the investigator as part of the initial responder classification for enrollment into the MPP sub-study will not be adjudicated by the CEC.

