6.1.2 Definition of Adverse Device Effect

An adverse device effect (ADE) is an AE that is related to the use of a medical device. This includes any AE resulting from insufficient or inadequate instructions for use or the deployment, implantation, installation, or operation, or any malfunctioning of a device and any event resulting from use error or from unintentional misuse of the device.

Adverse events, which result from the required medical procedures involved, when implanting, using or testing the respective device, even if not directly related to the device (e.g. anesthetic complications, wound healing disturbances, lead perforation, etc.) are considered ADEs.

Three categories for classification of relationship to the device and/or procedure are available:

- Clearly not related: A relationship of the AE to the device and / or procedure can be excluded.
- Possibly related: It cannot be excluded that there is a connection with the device under investigation and / or the procedure.
- Clearly related: A relationship of the AE to the device and/or procedure is likely/sure.

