6.3.2 Reporting Hospitalizations

To eliminate possible bias at the site level related to possible endpoint events of the MPP sub-study, adverse events requiring hospitalization for any cardiovascular hospitalizations and any other hospitalizations in which cardiovascular symptoms occur will be collected while subjects are enrolled in the MPP sub-study. Each hospitalization will be adjudicated to determine whether it meets the MPP sub-study endpoint criteria as a heart failure hospitalization by the Clinical Events Committee (CEC).

BIOTRONIK will be responsible for verifying completeness of the initial reported event and coordinating with sites to obtain any missing or additional source documentation required by the CEC to adjudicate the case. Additional documentation will be requested from the enrolling site as needed. The hospital report should include the following, if available:

- Discharge summary
- History and physical and admission summary
- Diagnostic and laboratory test results
- Chest X-ray, echocardiography, ultrasound or other imaging test results, as appropriate
- Consultations, operation reports, progress notes and discharge summaries from the subject medical records
- Investigator description and assessment of the event

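### Secondary Endpoint 1 counts a subject whose only qualifying event has an 'unknown' relation to MPP as free of events, which can only raise the reported AE-free rate

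*Combined protocol and SAP*

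**What the plan says.** Secondary Endpoint 1 (Summary and Section 2.1.2) is freedom from MPP-related complications at 6 months after MPP enrollment. Four provisions fix how it is calculated.

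- **Numerator, Section 2.6.** The AE-free rate "will be based on the total number of subjects with at least one MPP related adverse event" that needed invasive intervention to resolve.
- **Which verdicts count, Section 2.6.** "All adverse events which the CEC determines the event is related or possibly related to the MPP feature will be included" in the analysis. The next sentence removes the rest: "Adverse events with a final CEC adjudicated relation of not related or unknown will not contribute to or be included in the evaluation".
- **What the CEC sees and decides, Section 5.1.1.** For this endpoint it is to "adjudicate all adverse events that require additional invasive intervention to resolve which may be related to the MPP feature". Its scale has four levels: "The CEC will indicate whether the adverse event is related, possibly related, not related, or has an unknown relation to the MPP feature".
- **Population, Section 2.6.2.** Primary and secondary endpoints follow intention to treat, "utilizing all available data from fully enrolled subjects".

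No hypothesis, performance goal, alpha, confidence bound, expected rate or sample size is given for this endpoint. Section 2.6.1 on missing data deals only with NYHA class and the Patient Global Assessment. Neither an analysis that counts unknowns nor a report of their number is described.

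**The concern.** An 'unknown' verdict leaves the question of relation open, but the rule resolves it in one direction. Events reach the CEC for this endpoint only after two filters: an invasive intervention was needed, and a link to MPP was considered possible. Discarding an unresolved verdict on such an event puts it on the same footing as one where the link was rejected.

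The exclusion applies to events, not to subjects. The subject remains in the denominator and adds to the AE-free count. What is at stake is the accuracy of the reported rate in an FDA-required post-approval study. With no test attached, the estimate is itself the result that a reader takes away.

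**Working it through.** **Plan's own figures.** There is none for Secondary Endpoint 1 to reproduce. The documents supply only a scale for the denominator.

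- 90 evaluable subjects (Section 2.3.1.1), sized for the primary endpoint. An exact binomial test of 3% against 10% with n = 90 succeeds at 7 or more improved subjects. It has type I error 0.0188 and power 0.8075, so the figure reproduces.
- 100 enrolled after 10% loss (Section 2.5): 90 / (1 − 0.10) = 100.
- Up to 110 enrolled (Section 2.3).

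Because Section 2.6.2 includes all fully enrolled subjects, 100 planned and 110 at most are the relevant values. I carry 90 as the low end.

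**Notation.** n = subjects analysed; k = subjects with at least one related or possibly related qualifying event; u = further subjects whose only qualifying event is 'unknown'. The documents give neither k nor u, so all values below are assumptions.

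**Formulas.**

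- Plan's rule: rate = 1 − k/n
- Unknowns counted: rate = 1 − (k + u)/n
- Difference: u/n, which is never negative

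The plan's rate does not contain u at all. A subject who has both a counted and an unknown event is already in k and changes nothing. Two unknown events in one subject add 1 to u, not 2.

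**Shift per affected subject.** 1/90 = 1.1 points; 1/100 = 1.0 point; 1/110 = 0.9 points.

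**Illustration at n = 100.** Exact Clopper-Pearson 95% intervals are in brackets. They are added here for scale; the plan specifies no interval for this endpoint.

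| k | u | Plan's rule | Unknowns counted |
|---|---|---|---|
| 0 | 0 | 100.0% (96.4–100.0) | 100.0% (96.4–100.0) |
| 0 | 1 | 100.0% (96.4–100.0) | 99.0% (94.6–100.0) |
| 0 | 2 | 100.0% (96.4–100.0) | 98.0% (93.0–99.8) |
| 0 | 3 | 100.0% (96.4–100.0) | 97.0% (91.5–99.4) |
| 1 | 1 | 99.0% (94.6–100.0) | 98.0% (93.0–99.8) |
| 1 | 3 | 99.0% (94.6–100.0) | 96.0% (90.1–98.9) |

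The choice of denominator matters little. With k = 0 and u = 3, counting unknowns gives 96.7% at n = 90 and 97.3% at n = 110, against 100% under the plan's rule in both cases.

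**Where the true figure lies.** If the CEC's other verdicts are right, the rate that full information would give lies between the two columns. The plan reports only the upper end.

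**The case against.** The strongest reply is that the CEC scale already has a place for doubt. 'Possibly related' events count, so 'unknown' may be a small residual for which nothing can be said either way. The rule is also prespecified and openly stated. The CEC members are independent, are not investigators, and are blinded to site and subject identity (Section 5.1). Safety reporting is wider than this one rate: Section 6.2 collects all events related or possibly related to the implanted system, and Section 2.1.5 lists events attributed to MPP as data of interest. The rule takes an event out of a calculation, not out of the database.

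Most of this stands as a limit on size. It does not answer the point, because the plan keeps 'unknown' as a separate verdict, discards it, and provides no second rate or count to show the effect.

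Three stronger readings are tempting, and the documents do not support them.

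- **That poorer documentation earns a better rate.** Nothing says when the CEC uses 'unknown'; the adjudication process is left to a charter (Section 5.1). Incomplete records are one plausible cause. Section 6.3.2 makes the sponsor responsible for "coordinating with sites to obtain any missing or additional source documentation required by the CEC to adjudicate the case", although that text concerns hospitalizations.
- **That 'unknown' is by definition 'possibly related'.** Section 6.1.2 does say "Possibly related: It cannot be excluded that there is a connection with the device under investigation and / or the procedure", and an undetermined relation would fit those words. But that is a three-level device and procedure scale with no 'unknown' level, and it is not stated to govern the CEC's four-level MPP scale.
- **That one or two unknowns would be most of the safety information.** This presumes that few events are expected, and no expected rate is given.

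**Conclusion.** The concern holds as a one-directional bias in a descriptive estimate. By the plan's stated rule, a subject whose only qualifying event is 'unknown' is reported as AE-free, and nothing elsewhere in the documents overrides this. The size is u/n: about one percentage point per affected subject, and nothing if no unknowns occur. The range rests on assumed event counts and on a denominator between 90 and 110.

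A reader might infer that the rule could turn a failed safety endpoint into a passed one. It cannot, because no criterion is attached to Secondary Endpoint 1. The primary endpoint and the sample size are also untouched. The matter is still worth correcting: this is the only secondary endpoint devoted to safety, and the plan gives the reader no way to see how many subjects the rule affects.

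**What to change.** In Section 2.6, replace the exclusion sentence so that only events the CEC adjudicates as not related are left out of Secondary Endpoint 1, and events of unknown relation count together with those possibly related. Add that the AE-free rate without unknowns will be shown as a sensitivity result, and that the number of unknown events will be reported with a listing of each.

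If the sponsor prefers to keep the present rule for the main figure, prespecifying the rate with unknowns counted beside it, with the same count and listing, would remove most of the problem.

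The cost is a sentence or two. No new data, extra subjects or change to the CEC's categories is needed. The downside is that the headline rate may be slightly less favourable and may include some events that MPP did not cause, which is why both rates should be shown.

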Sentus QP – Extended CRT Evaluation with Quadripolar
Left Ventricular Leads

EP PASSION/MPP Sub-Study Amendment

Protocol Version – September 6, 2019

PROTOCOL SIGNATURE PAGE

The signature below documents receipt and review of the QP ExCELS study protocol and any attachments, and provides assurance that this study will be conducted according to all stipulations of the protocol, including all statements regarding confidentiality, and according to local legal and regulatory requirements and applicable guidelines.

Principal Investigator:

Name (please print)

Signature

Date

Summary

Title	Sentus QP – Extended CRT Evaluation with Quadripolar Left Ventricular Leads EP PASSION/MPP Sub-Study Amendment
Acronym	QP ExCELS
Subject collective	Heart failure subjects with standard CRT-D indication according to clinical routine.
Design	Single-arm, multi-center, and prospective trial. The MPP sub-study is designed to fulfill the FDA required post-approval study for the US market released BIOTRONIK MultiPole Pacing (MPP) feature (PMA P050023/S107) of the Ilivia HF-T QP family CRT-D system (PMA P050023/S103), or Acticor/Rivacor HF-T QP family CRT-D system (PMA P050023/S125).
Objectives	The primary objective of this clinical investigation is to convert a percentage of CRT non-responders to responders using the MultiPole Pacing (MPP) feature.
Primary Endpoint	Evaluation of the CRT responder status with the MPP feature
Secondary Endpoints	
 1. Freedom from MPP system-related complications at 6 months post MPP enrollment. 2. Clinical composite score + patient global assessment responder status 3. Clinical composite score responder status utilizing a modified responder classification
Sample Size	QP ExCELS study: up to 1,754 subjects enrolled in U.S. MPP sub-study: up to 110 subjects within the U.S. who are participating in the QP ExCELS study.
Investigational Sites	Up to 75 sites within the United States
Follow-up period	All subjects will be followed up to 6 months for screening into the MPP sub-study. If the MPP inclusion/exclusion criteria are met at screening, the subject will be followed an additional 6 months.
Sponsor	BIOTRONIK, Inc. Clinical Studies Department [name]

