The recent MultiPoint™ Pacing (MPP) IDE Study from St. Jude Medical showed that quadripolar multiple point LV pacing (MultiPoint™ Pacing algorithm) was non-inferior to standard quadripolar biventricular pacing. The multicenter study enrolled and followed 506 subjects with a standard CRT-D indication who were implanted with a CRT-D system (Quartet™ LV lead with a Quadra CRT-D) capable of delivering either quadripolar biventricular pacing or MPP. Quadripolar Bi-V pacing was activated at implant. At 3 months post-implant, patients' responder status was assessed, both responders and non-responders were randomized, and 1:1 randomization (Bi-V or MPP) was stratified by responder status. The primary efficacy endpoint (freedom from system-related complications through 9 months) was 93.2%, (97.5% lower confidence bound 90.4%) was greater than the objective performance criterion of 75%. The primary efficacy endpoint was met for both intention-to-treat and as-treated populations in 381 randomized patients (ITT, $p=0.013$ and as-treated, $p=0.008$, respectively). For patients in the MPP arm programmed with wide cathode spacing and the shortest intraventricular timing delay (5ms), MPP provided significantly higher clinical responder rate (between 3 and 9 months) up to 87% ($p=0.003$ vs $<30\text{mm}$) and converted 100% non-responders to responders ($p=0.006$ vs $<30\text{mm}$).

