2.1 Objectives

The primary objective of this clinical investigation is to demonstrate that the MPP feature is effective by converting a percentage of CRT non-responders to responders. Each subject's responder status will be assessed using a Clinical Composite Score (CCS) including three components: NYHA Class, heart failure (HF) hospitalizations, and cardiovascular death (Packer et al., 2001).

The MPP sub-study also includes three secondary endpoints.

2.1.1 Primary Endpoint 1

The purpose of primary endpoint 1 is to evaluate the CRT responder status with the MPP feature within the Ilivia 7 HF-T QP family CRT-D or Acticor/Rivacor 7 HF-T QP family CRT-D system, compared to a pre-specified performance goal.

The associated hypothesis is evaluated based on a CCS determining a responder classification based on changes in NYHA class, HF hospitalization, and cardiovascular death.

A responder status will be derived classifying these subjects as "Improved", "Worsened", or "Unchanged" using the following definitions.

Responder Classification at the 6-Month MPP Follow-up (evaluated compared to MPP enrollment visit):

- "Improved":
 - No HF hospitalization or cardiovascular death, AND
 - NYHA class is improved
- "Unchanged":
 - No HF hospitalization or cardiovascular death, AND
 - NYHA class is unchanged
- "Worsened":
 - HF hospitalization or cardiovascular death has occurred, OR
 - NYHA class is worsened

Ho: The proportion of subjects (P) who are classified as "Improved" is not superior to a performance goal (PG) of 3%.

$$PG \geq P$$

Ha: The proportion of subjects who are classified as "Improved" is superior to a performance goal of 3%.

$$PG < P$$

A rejection of the null hypothesis would indicate that the proportion of subjects classified as “Improved” is superior to 3%.

2.1.2 Secondary Endpoint 1

The purpose of Secondary Endpoint 1 is to evaluate adverse events that require additional invasive intervention to resolve, specifically related to the MPP feature of the Ilivia or Acticor/Rivacor HF-T QP family. These adverse events include any software issues related to MPP programming or any adverse event that occurs while MPP is enabled and that may be attributed to the use of the MPP feature.

2.1.3 Secondary Endpoint 2

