6.2 Reporting Adverse Events

The investigator has to record any reportable adverse event which occurs during study duration. The adverse event will be classified according to the seriousness, the relation to the implanted devices, and to the procedure. The investigator shall

report to the sponsor, by completing the appropriate eCRF, the following types of events:

- all adverse events related to or possibly related to the implanted system
- any major adverse events related to procedures involved with implanting, using, or testing the implanted system (examples are provided in Section 6.3.1 and definitions are provided in Appendix A: Definition of Terms)
- any adverse device effects, regardless of severity
- any cardiovascular hospitalizations and any other hospitalizations in which cardiovascular symptoms occur during participation in the MPP sub-study (Section 6.3.2 provides definitions)
- most recent heart failure hospitalization that occurs after eligible system implant and before MPP sub-study enrollment (if subject participates in the MPP sub-study; Section 6.1.4 provides definition)
- all adverse events that require additional invasive intervention to resolve, specifically related to the MPP feature of the CRT-D that occur during participation in the MPP sub-study (examples are provided in Section 6.3.3)

Events will be reported on an Adverse Event eCRF. Events should be reported as information is available, even if this results in an incomplete eCRF. The investigator must follow-up all ongoing reportable events either as long as the subject participates in the clinical investigation, the clinical investigation is terminated, or until the event has been resolved, whatever comes first.

The investigator must characterize each event by a single primary diagnosis. The primary diagnosis may describe an event consisting of several clinically recognizable features, symptoms or secondary diagnoses. Note: The observed symptoms and secondary diagnoses must be properly documented in the respective eCRF.

Multiple events may occur simultaneously in one subject. For each medically independent event with a primary diagnosis an individual report must be provided.

In addition, the action taken/treatment should also be provided with any supportive documentation available.

The investigator has to ensure that all relevant information is available. This also includes information from other parties (family, other hospitals, etc.).

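### Secondary Endpoint 1 leaves out events of unknown relation to MPP, so a subject whose only invasive event cannot be resolved counts as event-free

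*Combined protocol and SAP*

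**What the plan says.** Section 2.1.2 sets the purpose of Secondary Endpoint 1: to "evaluate adverse events that require additional invasive intervention to resolve, specifically related to the MPP feature". Section 2.6 turns this into a rate. "The AE-free rate calculated for secondary endpoint 1 will be based on the total number of subjects" with at least one MPP-related event needing invasive intervention.

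Section 5.1.1 describes the adjudication. The CEC receives events that needed additional invasive intervention and may be related to MPP, and gives one of four answers: "The CEC will indicate whether the adverse event is related, possibly related, not related, or has an unknown relation to the MPP feature". Section 2.6 counts the first two answers as events. For the other two it says: "Adverse events with a final CEC adjudicated relation of not related or unknown will not contribute to or be included in the evaluation".

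Neither section says what separates unknown from possibly related. Section 5.1 leaves the adjudication process to a CEC charter, which is not among these documents. No sensitivity analysis is planned for this endpoint, and it has no hypothesis, performance goal or sample size.

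The Summary names the same endpoint more loosely: "Freedom from MPP system-related complications at 6 months post MPP enrollment".

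**The concern.** In an event-free rate, leaving an event out is not neutral: unless the subject has another counted event, the subject moves into the event-free group. The events at issue are not a random mix of background illness. To reach the CEC, an event must already have needed an invasive procedure and been thought possibly attributable to MPP. An answer of unknown then means that the CEC did not rule the feature out. Section 2.6 nevertheless handles that answer as if it had been ruled out.

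The plan takes the cautious side for possibly related events, which count. Unknown is the neighbouring answer and goes the other way, with no stated boundary between the two. The choice of label for a doubtful case therefore decides whether it appears in the rate. What is at stake is the reported safety figure of an FDA-required post-approval study, and whether its reader can see how far it depends on unresolved cases.

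**Working it through.** **Inputs.** The plan gives no figure for Secondary Endpoint 1, so there is none to reproduce. The denominators come from the primary endpoint:

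- 90 evaluable subjects (2.3.1.1). This reproduces: with 90 subjects the exact test against 3% rejects at 7 or more responders, with one-sided error 0.0188 and power 80.8% at a true rate of 10%.
- 100 enrolled (2.5): 90 / (1 − 0.10) = 100.

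Section 2.6.2 analyses all fully enrolled subjects, so 100 is the more natural denominator. I show 90 as well.

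**Path of one event.**

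| Step | Section | Unresolved event |
|---|---|---|
| Needed invasive intervention and may be related to MPP | 5.1.1 | Goes to the CEC |
| CEC answer | 5.1.1 | Unknown |
| Counted in the rate? | 2.6 | No |
| Subject with no other counted event | 2.6 | Event-free |

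**Direction.** Let N be the number of subjects, C the number with at least one related or possibly related event, and U the number whose only events are of unknown relation.

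- Rate under 2.6: (N − C) / N
- Rate with unknown counted: (N − C − U) / N
- Difference: U / N, which is never negative

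A subject with both a counted and an unknown event is already in C, so nothing changes for that subject. The exclusion therefore raises the rate or leaves it alone.

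**Size per subject.** 1/100 = 1.0 percentage point; 1/90 = 1.1 points.

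**Illustration.** Take C = 0 and U = 0, 1 or 2. The values of C and U are assumptions, since the documents give none. Intervals are two-sided exact (Clopper-Pearson) 95%. The lower limit is the 0.025 quantile of Beta(N − U, U + 1); for U = 0 this is 0.025^(1/N), or 96.4% at N = 100.

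| U | 2.6, N = 100 | Unknown counted, N = 100 | 2.6, N = 90 | Unknown counted, N = 90 |
|---|---|---|---|---|
| 0 | 100% (96.4–100) | 100% (96.4–100) | 100% (96.0–100) | 100% (96.0–100) |
| 1 | 100% (96.4–100) | 99.0% (94.6–100.0) | 100% (96.0–100) | 98.9% (94.0–100.0) |
| 2 | 100% (96.4–100) | 98.0% (93.0–99.8) | 100% (96.0–100) | 97.8% (92.2–99.7) |

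Under 2.6 the three rows cannot be told apart. The two rates bracket the result: 2.6 gives the end at which no unknown event was due to MPP, and counting them gives the end at which all were.

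**The case against.** The best defence is that the rule is open, prespecified and consistent. Sections 2.1.2, 2.6, 5.1.1, the last reporting item in 6.2, and 6.3.3 all describe events tied to the MPP feature that need invasive intervention, and 2.6 uses the same four answers as 5.1.1. The charter may define unknown. Section 6.2 makes the investigator responsible for obtaining all relevant information, so unknown may be rare. Some unknown events will truly have nothing to do with MPP, and counting them all would then understate the rate.

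Most of this stands, and it limits the size of the point. It does not remove it. A charter can say when unknown applies, but the rule that such events do not count sits in 2.6. Uncertainty in both directions is a reason to show both rates.

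Four stronger readings are tempting, and the documents do not support them:

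- **That the Summary and 2.6 set rival rules.** The Summary line is a label without a counting rule, and the operative sections agree with one another.
- **That 6.1.2 contradicts 2.6.** Section 6.1.2 defines possibly related as "It cannot be excluded that there is a connection with the device under investigation" or the procedure, and has no unknown category. But it concerns relation to device and procedure and is used in investigator reporting; the endpoint uses CEC adjudication of relation to the MPP feature.
- **That lead and system events disappear from view.** Section 6.2 requires reporting of "all adverse events related to or possibly related to the implanted system", section 2.1.5 lists lead, generator and revision data for analysis, and section 5.1 puts events outside the sub-study's scope in the clinical report as reported by the site.
- **That the rate is to be set against the 93.2% in 1.2.1**, given there for "freedom from system-related complications through 9 months" in another manufacturer's study. The protocol makes no such comparison.

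Nor do the documents say that unknown means missing records. That poor documentation would improve the result is a plausible inference, not something the plan states.

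**Conclusion.** The concern holds as a minor point. Section 2.6 resolves every event of unknown relation in the device's favour, in a pool already limited to invasive events that may be due to MPP. The effect on the study's only safety rate is 1.0 percentage point per affected subject at N = 100 and 1.1 at N = 90, always upward or nil.

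This rests on the text of 2.6 and 5.1.1 and on simple arithmetic. The number of affected subjects is unknown and may be zero, in which case nothing changes. With no hypothesis or performance goal for this endpoint, no pass/fail decision is affected. The primary endpoint and the sample size are untouched.

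**What to change.** **Section 2.6.** Replace the sentence on excluded events with: *Events adjudicated as not related do not count. Events of unknown relation count as possibly related; the rate without them is reported as a sensitivity result.* If the sponsor prefers to keep the present rule for the main figure, the minimum is to report the rate both ways.

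**Section 5.1.1.** Add: *Unknown is used only when the source documents are insufficient to judge the relation.* Align the CEC charter with this.

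**Summary.** As a small wording alignment, replace the label with the 2.1.2 definition: freedom, through 6 months after MPP enrollment, from adverse events related to the MPP feature that require additional invasive intervention.

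**Cost.** Amendment wording in an FDA-required study and a charter check. No new data, no additional CEC cases and no change to the sample size are needed. The downside for the sponsor is that the reported rate can only stay the same or fall.
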